8.7 Duration of Follow-up for Adverse Events

The investigator will follow all unresolved AEs and SAEs until events are resolved or stabilized, patient is lost to follow-up, patient death, start of new oncology treatment, or end of study. Resolution of AEs and SAEs (with dates) should be documented in the appropriate CRF and in the patient’s medical record to facilitate source data verification. For SAEs, if, after follow-up, return to baseline status or stabilization cannot be established, an explanation should be recorded in additional case details section of the CRF.

For some SAEs, additional case details deemed necessary to appropriately evaluate SAE report (eg, hospital discharge summary, consultant report, or autopsy report) may be followed-up by telephone, fax, email, and/or a monitoring visit.

All pregnancies that occur during participation in the study should be followed to determine their outcome.

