4.4.2. Adverse Events (AEs)

All AEs will be coded from verbatim text to preferred term (PTs) and grouped by system organ class (SOC) using the Medical Dictionary for Regulatory Activities (MedDRA) version 27.1 or higher. AEs will be collected from the time of signature of informed consent throughout the treatment period. AEs will be graded by investigator according to National Cancer Institute (NCI) Common Terminology Criteria for Adverse Events (CTCAE) v5.0. Missing severity grade will not be imputed, and will be summarized as 'Missing Grade' category in the by-grade analysis.

An AE is considered a TEAE:

(i) If one of the criteria is met:

- 1) If the onset date is on or after the start of study treatment until 30 days after the last dose or prior to the start of a subsequent anti-tumor therapy (whichever comes first), or if the onset date is missing; or
- 2) If the AE has an onset date before the start of study treatment, but worsened in severity after the study drug administration (i.e. SAE start date is on or after the start of study

treatment until 30 days after the last dose or prior to the start of a subsequent anti-tumor therapy (whichever comes first);

(ii) Beyond 30 days after the last dose or after the start of a subsequent anti-tumor therapy (whichever comes first), treatment-related SAEs will also be considered as TEAEs.

Investigator assessed AEs causality to study drug will be classified as "Related" and "Not Related". An AE with a missing causality will be classified as "Related" to study drug.

Other AE variables include treatment-related AEs, AEs of special interest (AESI), COVID-19 related AEs, AEs leading to study drug modifications (i.e. dose interruption, dose reduction, or study drug withdrawal), AEs leading to death, and SAEs. The AESI information will be identified programmatically by SMQ/PT.

For AEs which are not on-going, duration of AE (days) is defined as AE end date – AE start date +1; for on-going AEs, the end date will be listed as 'Ongoing'.

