5.1.2.1. Adverse Events Start/End Date

AEs with onset/end dates that are partially/completely missing will be imputed as follows.

(i) AE start date:

- If the AE onset date is completely missing, the AE start date will be imputed as the reference start date;
- If the AE onset date is partial missing, then
 - If both the year and the month are available and the year and the month are the corresponding year and month of the reference start date, then the AE start date will be imputed as the reference start date;
 - If both the year and the month are available and the year and the month are not equal to the corresponding year and month of the reference start date, then the AE start date will be imputed as the 1st day of the month;
 - If only the year is available and the available year is the corresponding year of the reference start date, then the AE start date will be imputed as the reference start date;
 - If only the year is available, and the available year is not equal to the corresponding year of the reference start date, then the AE start date will be imputed as the January 1st of the year

(ii) AE end date will be imputed as below for the partial date only, the imputation rules only apply when the AE is not ongoing:

- If both the year and the month are available, AE end date will be imputed as the last day of the month;
- If only the year is available, AE end date will be imputed as the December 31st of the year.

If the imputed AE end date is after the death date for patients known to be dead at end of study or cut off date, the date of the death will be used for AE end date. If the imputed AE end date is after the last known alive date for patients alive at the end of study or cut off date, the date of last known alive date will be used for AE end date.

For AE continuing at the cut-off date, the end date will not be imputed and instead will be reported as “ongoing”.

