If a subject experienced the same adverse event (as identified by MedDRA preferred term) more than once during the study, the worst occurrence (e.g. worst grade) will be counted. Similarly, if a subject experienced more than one occurrence of the same SOC/PT, the worst occurrence (e.g. worst grade) will be counted within a particular SOC/PT. When summarizing AE by CTCAE grade, if a subject experienced more than one occurrence of the same SOC/PT, the worst severity grade will be counted. Each summary will be ordered by descending order of incidence of SOC and PT within each SOC. If the frequencies of SOC/PT tie, an alphabetic order of SOC/PT will be applied.

AESI Summary

AEs of special interest (AESI) are listed in the below table, and will be identified by MedDRA Query (SMQ)/PT:

AESI	Search Strategy
Abnormal hepatic function	Drug related hepatic disorders - comprehensive search (SMQ Code 20000006 Narrow search)
Differentiation syndrome	Differentiation syndrome (PT Code 10080638)

Abbreviations: AESI = adverse event of special interest; PT = preferred term; SMQ = standard MedDRA query.

All AESIs will be summarized in frequency and percentage by AESI category, PT and maximum CTCAE grade (All Grade, Grade ≥ 3 , Grade 1/2, Missing Grade). The following overall safety summary will also be summarized for each AESI category:

- AESI
- Treatment Related AESI
- AESI of CTCAE Grade 3 or higher
- AESI meeting SAE criteria
- AESI leading to dose modification
- AESI leading to dose reduction

- AESI leading to dose interruption
- AESI leading to dose discontinuation
- AESI leading to death

Moreover, time to AESI onset (days), AESI duration (days) and AESI outcome (the number and percent of patients) will be summarized descriptively.

Time to AESI onset is defined as the time interval from the date of first dose of study drug to the earliest onset date among all AESIs. That is, if a subject has multiple AESI occurrences, the earliest AESI onset date will be used as the onset date to calculate time to onset of AESI.

AESI duration (days) will only be calculated for ended AESI as (AE end date-AE start date+1).

Concomitant medication taken for hepatic function abnormal will be summarized by ATC and PT, and listed.

COVID-19 AE

COVID-19 AE will be identified by the following MedDRA Query (SMQ), and will be summarized (the number and percent of patients) by PT and maximum CTCAE grade (All Grade, Grade ≥ 3 , Grade 1/2, Missing Grade).

COVID-19	Search Strategy

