COVID-19	COVID-19 (SMQ Code 20000237 Narrow search)

AE Listing

All AE will be listed. All AE information including AE term, start date, end date, severity, whether the AE is DLT, CTCAE grade, whether the AE is SAE, classification of SAE (if SAE), whether the AE is AESI, relationship to study drug, action taken, outcome, whether this event is considered as part of Differentiation Syndrome will be presented in subject data listings. If the AE is ongoing at the data cut-off date, it will be reported as 'Ongoing' in the listing.

In addition, separate listings of (1) all TEAEs of CTCAE Grade 3 or higher, (2) all treatment related AEs, (3) all SAEs, (4) all AEs leading to discontinuation of study drug, (5) all AEs leading to dose modification, (6) all AEs leading to death, (7) all AESIs, (8) COVID-19 AEs will be provided.

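### AESI duration is summarised for resolved events only, so it will tend to understate how long these events last if any stay unresolved

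*SAP*

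**What the plan says.** SAP 5.2.11.2 names two AESI categories, abnormal hepatic function and differentiation syndrome. It plans this summary: "Moreover, time to AESI onset (days), AESI duration (days) and AESI outcome (the number and percent of patients) will be summarized descriptively". The duration rule follows: "AESI duration (days) will only be calculated for ended AESI as (AE end date-AE start date+1".

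Two other places in the SAP agree with it. Section 4.4.2 sets the general rule, "For AEs which are not on-going, duration of AE (days) is defined as AE end date" minus start date plus 1, and lists ongoing events as ongoing. Section 5.1.2.1 adds: "For AE continuing at the cut-off date, the end date will not be imputed and instead will be reported as" ongoing. No section specifies a Kaplan-Meier or other censored summary of AESI duration.

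Protocol 8.7 follows unresolved events until they resolve or stabilise, or until "patient is lost to follow-up, patient death, start of new oncology treatment, or end of study". An event can therefore reach the end of its follow-up without having resolved.

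**The concern.** An AESI that is still open has a known start date and a known minimum duration, so it is a right-censored observation. Leaving it out and describing the rest answers a narrower question: how long did events last, given that they were seen to end? Long events have more time in which follow-up can stop first, so resolved events are on average a shorter selection.

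The SAP handles the same data structure differently for efficacy. Duration of response (SAP 4.2.3 and 5.2.9.2) is analysed by Kaplan-Meier, and patients still in response are censored. Patients still in toxicity are left out of the duration statistic, and no reason is given.

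What is at stake is how two toxicities selected for dedicated reporting are described, in a study whose primary objective is safety. The more events fail to resolve, the shorter the reported duration tends to look. Open events are plausible here: Protocol 2.3.1 cites a median survival of about 1.5 months in refractory AML.

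**Working it through.** **No plan figure to reproduce.** The documents state no AESI duration and no number or share of AESIs left open. The figures below are assumptions chosen to show the range.

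**Inputs**
- Rule: resolved events only, end date minus start date plus 1 (SAP 5.2.11.2 and 4.4.2).
- Assumed true median duration: 14 days.
- Assumed share ongoing, f: about 7% to 60%.
- Assumed shapes: exponential, lognormal (sigma 1), Weibull (shape 2), each with independent exponential censoring.

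**Closed form, exponential case.** Let resolution have rate L and censoring rate M. Then f = M/(L+M). Durations among resolved events are exponential with rate L+M = L/(1−f). Hence resolved-only mean or median = (1−f) × true value.
- f = 0.25: 0.75 × 14 = 10.5 days.
- f = 0.40: 0.60 × 14 = 8.4 days.

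**Simulation, 400,000 events per scenario.** The Kaplan-Meier median with ongoing events censored was 14.0 days in every row.

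| Shape | Share ongoing | Resolved-only median (days) | Shortfall against 14 |
|---|---|---|---|
| Exponential | 9 / 25 / 40 / 57% | 12.7 / 10.5 / 8.4 / 6.0 | 9 / 25 / 40 / 57% |
| Lognormal | 10 / 27 / 42 / 60% | 12.8 / 11.1 / 9.4 / 7.6 | 9 / 21 / 33 / 46% |
| Weibull | 7 / 21 / 37 / 58% | 13.7 / 13.0 / 12.0 / 10.5 | 2 / 7 / 14 / 25% |

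The direction is the same in every row, but the size depends strongly on the shape. The rule that the shortfall equals the share ongoing belongs to the exponential case only.

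**Small cells, by hand.** Take resolved durations of 5, 8, 12 and 14 days. The ordinary median is (8+12)/2 = 10. Read as a Kaplan-Meier curve, with the median at the first time the curve reaches 0.5, these four give 3/4, then 2/4 at day 8: median 8.
- Add ongoing events at 40 and 60 days: 5/6, 4/6, 3/6 at day 12. The median moves from 8 to 12.
- Add ongoing events at 2 and 3 days instead: four remain at risk at day 5, so again 3/4, then 2/4 at day 8. The median stays at 8.

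Taking the midpoint where the curve sits exactly at 0.5 gives 10 for the four alone, 13 for the first addition and 10 for the second. Either way the comparison must use one convention; setting 10 against 8 would mix two. In general, Kaplan-Meier gives later resolved events at least as much weight as earlier ones. Its curve therefore never lies below the resolved-only curve from the same data.

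What is uncertain in a small cell is where the reported figure falls relative to the true value. In the exponential case, a cell with one resolved event reports more than the true median with probability 0.5^(1/(1−f)):
- f = 0.25: 0.5^1.333 = 0.40.
- f = 0.40: 0.5^1.667 = 0.31.

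**The case against.** The best reply is that nothing is hidden. The restriction to ended events is stated openly and matches the general AE rule. Ongoing AESIs still count in frequency, grade, seriousness, dose modification, death and time to onset. AESI outcome is tabulated beside duration, and every AESI is listed with open events marked. AESI duration is not among the primary endpoints named in SAP 2.1, no hypothesis is tested, and escalation rests on DLT counts and Safety Review Committee review. With about 24 to 30 evaluable escalation patients over eight cohorts, and one expansion patient (footnote to SAP Table 13), many cells will hold few AESIs or none. All of this stands and limits the severity. It does not correct the reported mean or median, and nothing requires the row to be labelled as resolved-only.

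A reader might also infer more than the documents support:
- **That the rule removes the longest events.** An event that began shortly before follow-up stopped is also ongoing. In simulated sets of 6 exponential events with at least one ongoing, the longest observed duration belonged to an ongoing event in only 31% of sets (25% ongoing) or 42% (40% ongoing).
- **That the excluded events cluster in patients who died or changed therapy.** Protocol 8.7 also stops follow-up at stabilisation, loss to follow-up and end of study. Protocol 6.1.19 follows drug-related AEs, and all SAEs, to resolution. Neither document gives counts or reasons.
- **That censoring at death settles the matter.** Death precludes resolution and is a competing event. Neither document says whether an AESI unresolved at death is closed or left open.

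**Conclusion.** The point holds, at minor severity. SAP 5.2.11.2 conditions AESI duration on resolution, and in expectation this understates typical duration whenever some AESIs stay open. It is tempting to state the understatement as a fact, or as equal to the share ongoing. The documents support neither: they do not show that any AESI will be ongoing at final database lock, and they give no share or distribution of durations. With none ongoing there is no bias. The illustrated 2% to 57% rests on an assumed 14-day median, the three assumed shapes and independent censoring. In very small cells the reported figure may fall on either side of the truth. Only the duration statistic is affected; no sample size, decision rule or other AESI output changes.

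**What to change.** In SAP 5.2.11.2:
1. Label the existing statistic as the duration of resolved AESIs. Print beside it the number of AESIs ongoing and the number unresolved at death.
2. Add a Kaplan-Meier median with 95% CI for time to resolution, for the pooled total and by dose level only where event numbers allow.
3. Censor ongoing AESIs at last follow-up, new anti-tumor therapy or cut-off. Treat death with the AESI unresolved as a stated competing event, reporting the cumulative incidence of resolution, or specify another rule explicitly.
4. Join successive records of one AESI that differ only in grade into one episode. Protocol 8.6.3 opens a new CRF entry at each change of severity, so one episode can otherwise count as several short ones.

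The cost is a short SAP paragraph and a little more programming, using a method the SAP already applies to response duration. No new data are needed. The median may be inestimable in small cohorts; there the counts and the AESI listing should carry the information.

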5.2.11.3. Death

Number of deaths and primary cause of death will be summarized descriptively. Similarly, the on-treatment deaths (i.e. deaths happening from first study drug administration to 30 days after the date of last administration of study drug or prior to the start of a subsequent anti-tumor therapy (whichever comes first)) and death during the follow-up period (i.e. deaths happening after 30 days after the date of last administration of study drug or prior to the start of a subsequent anti-tumor therapy (whichever comes first)) will also be tabulated.

All death information will be provided as patient list in which the on-treatment death will be flagged.

5.2.11.4. Laboratory Evaluations

For hematology, chemistry and coagulation labs, the observed values and change from baseline will be summarized by scheduled visit using descriptive statistics. For selected qualitative laboratory test (if any), number and percentage of patients with categorical results will be summarized for each scheduled visit.

Toxicities for clinical labs will be characterized according to NCI CTCAE, v5.0, and shift in grade from baseline to the worst post-baseline value will be summarized. Both the scheduled and unscheduled assessments will be used to identify the worst post-baseline values.

Shift table from baseline to worst post-baseline value according to abnormality (Normal / Abnormal, Not Clinically Significant / Abnormal, Clinically Significant) assessed by investigator will be provided.

The number and percentage of patients satisfying abnormal hepatic laboratory values categories defined in [Section 4.4.3](#) will be summarized.

Listings of all laboratory data with normal reference ranges, and CTCAE grades (when possible) will be provided.

5.2.11.5. ECG

Descriptive statistics will be presented for each ECG parameter for the observed values and change from baseline to post baseline by scheduled visits.

The criteria for potentially clinically significant findings are defined in [Table 11](#). The frequency and percentage of patients with any potentially clinically significant findings during the treatment period will be presented. The supportive data will be provided in patient data listings.

Moreover, the minimum, and maximum, and their corresponding change from baseline ECG parameter values will be summarized descriptively overall treatment period.

Shift table from baseline to worst post-baseline value according to abnormality (Normal / Abnormal, Not Clinically Significant / Abnormal, Clinically Significant) assessed by investigator will be provided.

A listing of all ECG data will be provided.

5.2.11.6. Vital Signs

For vital sign parameters (Systolic Blood Pressure, Diastolic Blood Pressure, Pulse Rate, Temperature, and Weight) the observed values and change from baseline will be summarized by scheduled visits using descriptive statistics during the treatment period.

Additionally, the frequency and percentage of patients with any potentially clinically significant findings (defined in [Table 12](#)) during the overall treatment period will be presented.

Moreover, the minimum, and maximum, and their corresponding change from baseline vital sign values will be summarized descriptively overall treatment period.

A listing of all vital sign data will be provided.

5.2.11.7. Performance Status

The frequency and percentage of patients for each ECOG score level will be summarized by scheduled visit and by maximum post-baseline score during the treatment period. Shift in grade from baseline to the maximum post-baseline score will be summarized.

A listing of ECOG score for all patients will be provided.

5.2.11.8. Echocardiogram

A by-patients listing of ECHO/MUGA values at each time point will be listed.

5.2.11.9. Differentiation Syndrome

Besides DS analysis as an AESI category described in [Section 5.2.11.1](#), the following analysis will also be provided.

The number and percent of patients experiencing differentiation syndrome (DS) will be summarized. The number and percent of patients with following DS symptoms will be summarized:

- Dyspnea
- Unexplained fever
- Weight gain
- Unexplained Hypotension
- Acute renal failure
- Interstitial lung infiltration or pericardial effusion

In addition, the number and percent of patients with the Montesinos grading will also be summarized, the grading includes two grade level as moderate (2-3 symptoms) and severe (4 or more symptoms).

DS will be summarized by symptoms, Montesinos grade, and CTCAE grade.

Concomitant medication taken for DS will be summarized by ATC and PT, and listed.

A by-patients listing of differentiation syndrome will be listed.

5.2.11.10. Physical Examination, Ophthalmologic Examination

A listing of physical examination data, ophthalmologic examination data for all patients will be provided (where available).

5.3. Subgroup Analyses

Not applicable.

5.4. Other Analyses

5.4.1. Gene Mutational Analysis

The number and percent of patients with gene mutation and rearrangement for AML patients will be summarized, a patient with multiple gene mutation and rearrangement will be counted in each category. A listing of gene mutational data for all patients will be provided.

6. PLANNED ANALYSIS

6.1. Interim Analysis

No formal interim analysis is planned for the study. However, the accrued data from any cohort may be analyzed for internal decision-making purposes, for example, to provide information for a potential phase 3 study design.

6.2. Final Analysis

The final analysis will be conducted after final Database Lock (DBL) for this study.

7. CHANGE FROM THE PROTOCOL

Here is a list of changes in this analysis plan compared with the protocol

- Added All Subject Set for pre-screening and screening summaries.
- Added Efficacy Analysis Set as primary analysis set for efficacy analysis and clarified definition of Response Evaluable Analysis Set as single dose from the PK week might not be an effective treatment. Safety Analysis Set was the primary set for safety analysis.
- The DLT- evaluable analysis set definition in the protocol is to include all patients enrolled into dose escalation part of the study who (i) either received at least 75% of the assigned doses of the HMPL-306 during the DLT assessment window (i.e. Cycle 1 Day 1 [C1D1] through C1D28) or (ii) experienced a DLT in Cycle 1. However, since these criteria have been incorporated in the SRC review, the DLT-evaluable analysis set will be based on the decision from the SRC review.
- Removed DLT-equivalent analysis as investigator's evaluation of each AE satisfying DLT criteria or not was not well documented in EDC.
- Patients enrolled were summarized based on all subject set instead of safety analysis set.
- Removed Rate of CR+CRh, duration of CR+CRh and time to CR+CRh endpoints, since cCR-2 (rate of CRM RD+CR+CRh) and cCR-3 (rate of CRM RD+CR) are more meaningful.
- Removed Time to Hematologic Recurrence endpoint as it has the similar rationale for DOcCR1.
- Removed Disease Free Survival (DFS) endpoint as it has the same rationale for DOcCR1.

